2.0 Objectives

- The **primary objective** of the study is to assess the effectiveness of the **mychoice** mHealth tool on perceived patient self-efficacy and decisional conflict, and whether these results are enhanced in minority patients.
- The **secondary objective** of the study is to describe the acceptability and feasibility of implementing **mychoice** in oncology services at three leading cancer centers in Philadelphia.
- **Purpose of the study:** **mychoice** was conceptualized and developed with a Fox Chase-Temple NODAL grant, using extensive formative research, including the use of commercial marketing techniques (perceptual mapping and vector modeling) and

patient engagement, and customized to address the significant barriers for African American patients to consider clinical trials. The tool went through user testing and received excellent reviews, and now is ready for an efficacy test. This study represents the next step in personalized clinical trial education research. It completes the **mychoice** communication tool to make it multi-cultural and thus appropriate for all patients, and tests its effectiveness with diverse cancer patients to improve knowledge and preparation to discuss clinical trials within real world settings. We will also explore organizational factors that impact implementation of a technology-based intervention, an innovative aspect that will provide critical understanding on feasibility to ensure scalability in a large medical setting. Results could inform how a tool like **mychoice** could be implemented in a cancer center and enhance communication about clinical trials between patients and doctors.

- **Specific Aims:**

- **AIM 1:** Test the perceived usefulness and effectiveness of **mychoice** to increase patients' self-efficacy and decrease decisional conflict.
 - **AIM 2:** Describe the acceptability and feasibility of implementing **mychoice** in oncology services at three leading cancer centers in Philadelphia by identifying provider and organizational factors influencing its integration in the clinical space.
- The following **hypotheses** are proposed for Specific Aim 1:
 - **H1:** Compared to a non-tailored education aid, **mychoice** will improve self-efficacy in making a decision about participating in clinical trials for all patients as well as a subsample of underrepresented patients (non-white).

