 - **H2:** Compared to a non-tailored education aid, **mychoice** will reduce decisional conflict about clinical trial participation for all patients, as well as a subsample of underrepresented patients (non-white).

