The primary outcomes are decision-related self-efficacy and decisional conflict. Secondary measures will include patient-related outcomes such as increased knowledge, use of **mychoice**, increased patient activation, and perceptions of the provider encounter. Table 1 on the following page describes the study measures.

- o **Randomization.** Upon completing the informed consent form, patients will be randomized to either **mychoice** group or control group by RedCAP at a 1:1 ratio. The system will randomly assign participants as they enter into the system after they have been consented to the study.

Table 1. RCT Study Measures

Measure	Source	Description	Pre	Post	1 month follow-up
Demographics	NIH	Age, education, insurance, income, race, ethnicity, gender, living situation (8 items)	X		
Cancer and Clinical Trial Experience (personal and family/friends)		Cancer type, stage (6 items)	X		
Technology Use	HINTS	Mobile, smartphone, computer, tablet (5 items)	X		
Health Literacy	SILS	1 item	X		
Clinical Trial Perceptions	[name], [name]	Test perceptions over time using perceptual mapping – knowledge, benefits, concerns, perceptions/experiences with cancer treatment, beliefs about health care providers and your health (48 items pre; 31 post; 43 follow up)	X		X
Patient Activation (Decisional Engagement Scale)	Hoerger, et al (DES-10)	2- scales decision making preference (1 item), Comfort with interacting with physician (10 items)	X		X
Patient Self-Advocacy Scale	Brashers et al.	Perceptions and self-reported behaviors about information seeking and provider relationship (12 items)	X		
Knowledge of Clinical Trials	Campbell	Knowledge of clinical trials (reduced items; 16)	X	X	X
Self-Efficacy	PEPPI	Confidence in communicating with Physician (10 items)	X	X	X
Decision preparation scale (PrepDM)	Bennett, et al	Value of mychoice in preparation to make a decision (10 items)		X	
Perceived Shared Decision Making (CollaboRATE)	Barr, et al	Patient perceptions of effort to discuss concerns			X
Shared Decision Making	SDM Q-9 Kriston et al	Patient perception of shared decision making with provider (12 items)			X
Decisional conflict	Ottawa	Decision conflict (revised; 13 items)	X	X	X
Clinical Trial Intention	Adapted from Ottawa Patient Decision Aid	If offered, would be considered (1 item)	X	X	X
Satisfaction with patient materials	CISRC adapted	Helpfulness and recommendations of materials (app or standard brochure) (3 items post; 13 items follow-up)		X	X

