13.0 Statistical Analysis

- **General analyses:** After screening for potential differences across sites on the key outcome variables, all data will be graphed and tabulated by group (i.e., **mychoice** vs. control) for review of distributional properties and anomalous values prior to the main analyses. Continuous and normally distributed variables will be summarized with means and standard deviations. All parameter estimates will be bound by 95% confidence intervals. Tests of significance will be based on adjustments for alpha to protect family-wise error rates at 5% using the method of Benjamini and Hochberg [40]. Data will be analyzed using an intent-to-treat (ITT) approach where subjects are analyzed according to their treatment assignment at randomization, regardless of level of participation or engagement. Because an ITT analysis is planned, we will evaluate models suitable for non-ignorable (missing not at random) data within a sensitivity analysis framework in order to determine the extent to which analysis conclusions depend on the assumptions being made about unobserved values. We will perform model-based analyses with direct maximum likelihood methods, including those for data missing not at random (MNAR) if necessary. We will screen for violations of assumptions for all statistical tests involved. All analyses for specific aims will be conducted using SAS 9.4.

- **H1 Analysis:** The principle endpoint will be 1-month follow-up, i.e., one month after completion of either the **mychoice** or control education. We will conduct a mixed-effect regression models for each repeatedly measured continuous outcome (i.e., self-efficacy and decisional conflict at post intervention and 1-month follow-up) on a dummy grouping variable (**mychoice**, as compared to Control), adjusting for baseline level of this outcome and covariates discovered to be unbalanced between the two groups, and moderators of interest. In these models, we will treat time as a categorical variable and examine the fixed effects for time, intervention group, and their interactions. We will specify the covariance structure within patients using an unstructured model to account for the in-patient correlation over time.

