In addition, the dichotomous race (White vs. non-White) variable and the non-White-Treatment interaction will be entered in each regression model as predictors, to understand possible different effects of **mychoice** for non-White vs. White participants. A significant, positive regression coefficient of the non-White Treatment interaction indicates non-white participants' benefits more from the treatment than their White counterparts.

- **Power:** Power analyses were performed using G*Power 3.1, with 2-sided tests and an adjusted alpha level of .025 (= .05/2) for multiple group comparisons. We performed power analyses for comparisons on primary and secondary outcomes for Aim 1. Effect size (mean difference between groups divided by the pooled standard deviation) is a common measure for assessing the magnitude of a treatment effect on continuous outcomes. The number of participants needed for Aim 1 is selected to sufficiently power the detection of a difference between groups on the outcomes adjusting for covariates and moderators at 1-month follow-up.

To detect a moderate treatment effect size of 0.47 SD on either the self-efficacy and decisional conflict scales, our trial would need 88 patients per group, presuming alpha = .025 and beta = .20 (power = 80%). Of note, this effect size is comparable to prior studies (please cite some papers). Including a 20% adjustment for dropout and loss of degrees of freedom when adjusting for possible additional confounding variables, a total of 220 patients are needed. By using mixed-effects repeated measures regression analysis, our power is likely to be even higher. Therefore our estimated power provides a conservative lower-bound of the likely actual power of our sample size. Also, we will need an additional 50 patients to do exploratory analysis on potential differences in effect by recruitment type, bringing the total needed to 270.

- **H2 Analysis:** Descriptive statistics will be employed for the analysis of the quantitative feasibility and acceptability data. All qualitative data collected through the meeting notes and debriefing interviews will analyzed the Krueger method of analyzing narrative data will be used; familiarization, identifying a thematic framework indexing, charting, mapping and interpretation [80]. Recordings will be listened to and transcriptions read to become familiar with what participants said. A

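### The single sign rule for the non-White-by-treatment interaction points the wrong way for decisional conflict, so less non-White benefit would be read as more

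*Combined protocol and SAP*

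**What the plan says.** Section 13.0 (H1 Analysis) fits a mixed model to each repeatedly measured continuous outcome, named as "self-efficacy and decisional conflict at post intervention and 1-month follow-up". Treatment is a dummy variable, mychoice against control. The next paragraph adds race, White against non-White, and says that the race-by-treatment "interaction will be entered in each regression model as predictors". It then gives one reading rule, with no outcome named: "A significant, positive regression coefficient of the non-White Treatment interaction indicates non-white" participants gain more from the intervention than White participants.

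Section 2.0 sets the direction of benefit. Aim 1 is to increase patients' "self-efficacy and decrease decisional conflict". H2 again predicts a reduction in decisional conflict, including in the non-white subsample. The primary objective asks about the effect on both outcomes "and whether these results are enhanced in minority patients".

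On the scale itself, Table 1 in Section 4.0 names the Ottawa source and says "Decision conflict (revised; 13 items". It gives no scoring direction and mentions no reverse-scoring.

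**The concern.** The two primary outcomes improve in opposite directions, so one positive-sign rule cannot serve both unless one scale is reversed before modelling. The documents do not say that this is done.

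For decisional conflict the rule fails in two ways. It labels a significant positive coefficient as greater non-White benefit when it means less. It also says nothing about a significant negative coefficient, which is the result that would support the hypothesis of enhanced benefit.

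At stake is the part of the primary objective that concerns minority patients, the group whose barriers the tool was first built to address. This sentence is the only explicit criterion for that claim. The paragraph headed H2 Analysis in Section 13.0 does not supply another, because it covers feasibility, acceptability and qualitative data.

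**Working it through.** **The plan's own figure.** Section 13.0 states 88 per group for 0.47 SD at two-sided .025 with 80% power. The two-sample t calculation gives 88 (power 80.3%), and 2 × 88 / 0.8 = 220. Both figures reproduce, and neither depends on the point made here.

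**Sign of the coefficient.** Code mychoice = 1 and non-White = 1. The second code is implied by the name of the term and by the rule being right for self-efficacy. Then:

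interaction = (mychoice − control in non-White) − (mychoice − control in White)

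The planning effect of 0.47 SD is used to build an example for decisional conflict, taking higher as more conflict. With 20% non-White (Section 4.0), an overall effect of −0.47 and an interaction of +0.40, the White effect w solves 0.8w + 0.2(w + 0.40) = −0.47. This gives w = −0.55 and a non-White effect of −0.15. The mirror case, −0.40, gives w = −0.39 and −0.79. The self-efficacy row uses the same sizes with positive signs.

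| Outcome | White | Non-White | Interaction | True meaning | What the rule says if significant |
|---|---|---|---|---|---|
| Self-efficacy | +0.39 | +0.79 | +0.40 | non-White benefit more | more (correct) |
| Decisional conflict | −0.55 | −0.15 | +0.40 | non-White benefit less | more (wrong) |
| Decisional conflict | −0.39 | −0.79 | −0.40 | non-White benefit more | nothing |

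Recoding race does not help. With White = 1 every sign flips, and the rule is then wrong for self-efficacy instead.

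**How often the rule would fire.** Assumptions: outcome SD 1, 1:1 allocation within race, a single time point, and 20% loss from 270, so 216 analysed (43.2 non-White, 172.8 White). R² is the share of variance explained by baseline.

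SE = √[(4/43.2 + 4/172.8)(1 − R²)]

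- R² = 0: SE = √(0.0926 + 0.0231) = 0.340.
- R² = 0.36 (assumed): SE = 0.8 × 0.340 = 0.272.

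The threshold is z × SE, with z = 1.960 at .05 and 2.241 at .025. The probability of a significant positive result for a true +0.40 is Φ[(0.40 − threshold)/SE]. Both levels are shown because the power section uses .025, while the tests are to be adjusted by Benjamini-Hochberg.

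| Analysed | R² | SE | Threshold, .05 | Probability, .05 | Threshold, .025 | Probability, .025 |
|---|---|---|---|---|---|---|
| 216 | 0 | 0.340 | 0.667 | 22% | 0.763 | 14% |
| 216 | 0.36 | 0.272 | 0.533 | 31% | 0.610 | 22% |
| 270 (no loss) | 0 | 0.304 | 0.596 | 26% | – | – |
| 270 (no loss) | 0.36 | 0.243 | 0.477 | 38% | – | – |

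A simulation of 20,000 trials (216 analysed, 43 non-White, R² = 0, two-sided .05) agreed. A true +0.4 gave a mean coefficient of +0.401, significant and positive in 21.7% of trials. A true −0.4 gave a significant negative coefficient in 21.7%, a result on which the rule is silent.

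**The case against.** The strongest reply is that the sentence only explains a coefficient. It controls no test, alpha level or dataset. The stated purpose of the race analysis is non-directional, the power section uses two-sided tests, and "All parameter estimates will be bound by 95% confidence intervals". A careful analyst who has read H2 knows that a fall in conflict is good and would see a significant negative interaction for what it is. This stands in part. The misreading is not certain, the estimate and its interval would still show the effect, and H2 gives a reader the means to interpret a negative coefficient. But a prespecified rule should not need the analyst to depart from it, and a sign settled after the data are seen is open to challenge.

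The second reply is that the scoring direction is unverified. The survey instruments are listed as appendices but their content is not in the text available here. If the revised scale is scored so that higher is better, the rule is correct. This stands as a condition on the conclusion. Reducing decisional conflict most naturally means lowering the score, and the plan does not say otherwise. If the scale is reversed, Section 13.0 still omits the fact needed to apply its own rule.

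The third reply concerns the size. The interaction of +0.40 SD and the R² are assumed, the calculation uses one time point where the plan has two, and Section 13.0 applies its 20% allowance to reach 220 before adding 50. These points are fair: the probabilities illustrate scale and do not describe the planned model exactly. A true +0.8 SD would raise the probability to 65% (R² = 0) or 84% (R² = 0.36) at .05. With an overall effect of −0.47, however, it implies −0.63 in White and +0.17 in non-White patients, so conflict would rise in the latter. That case is extreme, and the conclusion does not rely on it.

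**Conclusion.** The concern holds. Followed as written, the rule is right for self-efficacy and gives the opposite of the correct conclusion for decisional conflict, a primary outcome within the primary objective. This rests on two readings that the documents support but do not spell out: non-White is coded 1, and a higher score means more conflict.

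The consequence is limited to the race-by-treatment result for decisional conflict, and it arises only when that term is significant. For a true +0.40 SD with 216 analysed, that is 14% to 31% of trials across the two alpha levels and the assumed R² of 0 to 0.36. The low power limits how often the rule is used; it does not make the rule right. The point should be corrected before analysis.

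**What to change.** In Section 13.0, replace the sentence with one that gives the favourable sign for each outcome, for example:

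> For self-efficacy, a positive non-White-by-treatment coefficient indicates greater benefit in non-White participants; for decisional conflict, scored so that higher means more conflict, a negative coefficient does.

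Alternatively, state that decisional conflict is reverse-scored before modelling, so that one rule fits both outcomes. In either case, state the scoring direction of the revised 13-item scale and the coding of the race variable.

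The cost is a sentence or two of text. Data collection, model fitting, sample size and timeline do not change.

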14.0 Data Safety Monitoring Plan

- This is a minimal risk study. We will monitor the study and any participant complaints or issues. In general, we believe data will be accurate based on self-reported attitudes.

15.0 Adverse Event Reporting

- In accordance with FCCC guidelines, this protocol will employ the following mechanisms for adverse event reporting: 1) alert the FCCC review committees of any and all reports of adverse events; 2) inform all members of the study team of any all reports of adverse events. If 3 or more adverse events are reported, the study team will assess potential causes of the adverse events and, if events are clearly linked to study participation, discontinue the study.

16.0 Quality Assurance Procedures and Participant Confidentiality

- Information about study subjects will be kept confidential and managed according to the requirements of the Health Insurance Portability and Accountability Act of 1996 (HIPAA). Those regulations require a signed subject authorization informing the subject of the following: The protected health information (PHI) that will be collected from patient; who will have access to that information and why; who will use or disclose that information; the rights of a research subject to revoke their authorization or use their PHI. In the event that a participant revokes authorization to collect or use PHI, the investigator, by regulation, retains the ability to use all information prior to the revocation of subject authorization. To ensure confidentiality, only a participant identifier will be recorded and used with collected electronic data. All records will be secured in a locked location.
- While we will not access private health information during the study accrual, but may access information on their participation in a clinical trial when we are analyzing data while the IRB is still open. As a result we will maintain the HIPAA waiver in the consent process.

17.0 Participant Informed Consent

- See separate informed consent document

19.0 Appendices

- A: Patient Card
- B: Flyer
- C. Script for electronic informed consent
- D: Baseline Survey
- E: Post Test Survey
- F: Follow-up Survey – Treatment Arm
- G: Follow-up Survey – Control Arm
- H: Physician Survey – Pre Intervention
